3.2. Start of Study and End of Study Definitions

The start of the study is defined as the date the first enrolled subject signs an Informed Consent Form (ICF). The point of enrollment occurs at the time of subject number allocation. The end of the study is defined as the date of the last subject's last assessment (scheduled or unscheduled).

3.3. Additional Groups

Following review of the safety, tolerability, PK, and PD data (where systemic exposure is not expected to exceed that stated in the dose escalation stopping criteria [[Section 3.7](#)]), additional dose groups may be added to the study.

Up to 2 additional groups of 8 subjects (6 active: 2 placebo) may be included in Part B. The requirement for additional groups will be agreed with the Sponsor and documented in the Trial Master File (TMF).

3.4. Discussion of Study Design, Including the Choice of Control Groups

For both parts of the study, a sequential-group, ascending-dose design has been chosen for safety reasons as OLP-1002 is in the early stages of clinical development, with Part A of the study being the first time it will be administered to humans. Subcutaneous doses have been chosen for both parts of the study, as this is the intended clinical route of administration.

In Part A, safety data up to Day 10 will be reviewed prior to dose escalation, and PK data up to Day 7 will be reviewed for all groups receiving $\geq 12 \mu\text{g}$ OLP-1002. In Part B, safety, tolerability and PK data up to Day 22 will be reviewed for all dose groups. As the $t_{1/2}$ of OLP-1002 is predicted to be approximately 180 hours (based on non-clinical data) review of

safety data up to Day 10 (Part A) and Day 22 (Part B) is considered sufficient to ensure data from at least one half-life is included in the review. In addition, as plasma exposures are anticipated to be low, it is expected that it will only be possible to perform an assessment of peak concentrations (C_{max}) and therefore PK data to Day 7 (Part A) and Day 22 (Part B) will be sufficient. Additionally, a cumulative safety review will occur such that additional emerging safety data from earlier groups will be considered when making a dose escalation decision.

Healthy male and female subjects will be recruited into this study. The inclusion of females of childbearing potential is in accordance with International Council for Harmonisation (ICH) M3, based on the short dosing duration (< 2 weeks).

In Part A, it is anticipated that groups of 4 subjects (3 active: 1 placebo) will be sufficient in order to determine safety and tolerability. In order to assess the PD effects of OLP-1002, 6 groups in Part A will include 8 subjects (6 active; 2 placebo). A full review of the safety and tolerability data from Part A will be performed to determine the dose regimen for Part B. Part B may start after a full review of all safety and tolerability data from Group A1 to A6. A review of PD data may also be performed, at the discretion of the Investigator. Details of the dosing regimen and duration used for Part B of the study will be documented in the TMF.

Based upon the nonclinical data, the duration of a 28-day follow-up in Part A, and a 57-day follow-up in Part B is considered adequate to achieve the study objectives.

Pharmacokinetic analysis in Part A will initially only be conducted for groups receiving $\geq 12 \mu\text{g}$ OLP-1002, with retrospective analyses of samples from lower dose groups occurring in the event of PK data being quantifiable at doses $\geq 12 \mu\text{g}$ and if supported by bioanalytical stability data. Dose escalation decisions for doses $< 12 \mu\text{g}$ in Part A will not require PK data. The rationale for this is that maximum plasma concentrations at $12 \mu\text{g}$ are expected to be approximately 0.078 ng/mL and the bioanalytical method used for preclinical species has a lower limit of quantification (LLOQ) of 5 ng/mL. The increased sample volume possible from humans (compared to small animals) may afford an approximate 10-fold increase in sensitivity with possibly an additional 5-fold increase from the use of a more sensitive mass spectrometer. Additional optimization of the PK analysis has delivered an LLOQ of around 1 ng/mL with the limit of detection being 0.2 ng/mL. Therefore, even with the increased assay sensitivity plasma levels from doses at or below $12 \mu\text{g}$ are not expected to be quantifiable. It is apparent from the predicted plasma concentrations (see [Section 3.5.2](#)) that only a small number of samples around C_{max} at the highest dose would be quantifiable and that a conventional approach to pharmacokinetic will not achieve a full definition of the plasma concentration vs time profile or enable an estimation of the terminal phase. In addition the planned dose levels have a high safety margin when comparing the predicted exposures to the exposures at the NOAEL (see [Section 3.5.2](#)), with the $12 \mu\text{g}$ dose level having an expected 312-fold and 255-fold safety margin based on C_{max} and $AUC_{0-\infty}$, respectively. Therefore, if exposure is significantly higher than predicted it is not expected to exceed the PK stopping criteria.

This study will be double-blind and placebo-controlled in order to avoid bias in the collection and evaluation of data during its conduct. Placebo has been chosen as the control treatment to

assess whether any observed effects are treatment-related or simply reflect the study conditions.

Conducting the study in healthy subjects mitigates the potential confounding effects of the disease state and concomitant medications.

Continuous ECG monitoring will be recorded in this study and archived for potential future analysis of OLP-1002 effects on the QT interval, with a view of supporting a potential thorough QT study waiver.

3.4.1. Dose Interval

Following thorough review of all available nonclinical data (pharmacological and toxicological), dosing in Part A for groups consisting of 4 subjects will be such that there will be 48 hours between the first and second subjects, and 48 hours between the second and remaining 2 subjects in each group. For groups in Part A consisting of 8 subjects, 2 subjects (1 active: 1 placebo) will be dosed 48 hours prior to the remaining 6 subjects.

In Part B, sentinel dosing will be used in groups where exposure to OLP-1002 at steady state is predicted to exceed exposures that have been shown to be safe and well tolerated in earlier groups in Parts A or B. When used, two subjects (1 active; 1 placebo), will be dosed 4 days prior to the remaining 6 subjects (5 active; 2 placebo). The 2 sentinel subjects will always be 2 doses ahead of the remaining subjects (ie. sentinel subjects will receive dose 2 before the remaining subjects receive dose 1). Subjects in groups where exposure is not predicted to exceed that tested in Part A will be dosed on the same day. Accumulation of OLP-1002 is expected following multiple doses, based on the preclinical data, and will be taken into account when determining the doses for Part B (see [Section 3.5.3](#)). If it is not possible to quantify exposure it will be assumed that multiple dosing results in a 4-fold accumulation based on the predicted $t_{1/2}$ of 180h.

In Parts A and B, there will be a minimum interval of a 10-minute gap between dosing subjects (when dosed on the same day). Continuation to dose the remaining subjects in a group will be at the Investigator's discretion.

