3.1.2. Part B

Part B will comprise a multiple-dose, sequential-group study. Overall, 32 subjects will be studied in 4 groups (Groups B1 to B4), with each group consisting of 8 subjects. Up to 2 additional groups (16 subjects in total) may be included for further assessment of safety and tolerability ([Section 3.3](#)).

Potential subjects will be screened to assess their eligibility to enter the study within 28 days prior to the first dose administration. Each subject will participate in 1 treatment period only and reside at the CRU from Day -1 until Day 15.

All subjects will return for non-residential visits on Days 18 (± 2 days), 22 (± 2 days), 25 (± 2 days), and 29 (± 2 days), and for a poststudy visit on Day 57 (± 2 days).

[figure not shown]
In each of Groups B1 to B4, 6 subjects will receive OLP-1002 and 2 subjects will receive placebo. For all subjects, a single subcutaneous dose will be administered on Days 1, 4, 7, 10, and 13. Prior to each dosing occasion a physician will review the available safety and tolerability data from each subject to confirm it is acceptable to continue dosing. The dosing frequency in Part B may be changed following review of data from groups in Part A ([Section 3.4](#)).

Sentinel dosing will only occur in Part B at dose levels where exposure to OLP-1002 at steady state is predicted to exceed exposures that have been shown to be safe and well tolerated in earlier groups in Parts A or B. In the event of sentinel dosing, 2 subjects (1 active, 1 placebo) will be dosed at least 4 days prior to the remaining 6 subjects (5 active: 1 placebo). Safety data for the sentinel subjects from at least 2 additional doses will be reviewed prior to dosing the remaining subjects (i.e. sentinel subjects' safety data after doses 1 and 2 will be reviewed prior to the remaining subjects receiving dose 1). In addition, safety data from each subject will be reviewed by a physician prior to each dose to approve continued dosing.

Doses will be administered in an escalating manner following satisfactory review of safety, tolerability, and PK data up to Day 22 (216 hours post-final dose) from the lower dose levels. Part B may start after a review of the safety, tolerability, and available PK for Groups A1 to A6. The total daily dose administered will not exceed the highest single dose given in Part A.

An overview of the study design is shown in [Figure 2](#).

Figure 2: Study Schematic (Part B)

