3.5.3. Proposed Doses

The proposed IMP dose levels for Parts A and B are shown in [Table 3](#).

Table 3: Proposed Investigational Medicinal Product Dose Levels for Parts A and B

Study Part	Group	Dose (OLP-1002)
Part A	A1	30 ng or placebo
	A2	120 ng or placebo
	A3	400 ng or placebo
	A4	1.2 µg or placebo
	A5	3 µg or placebo
	A6	6 µg or placebo
	A7	12 µg or placebo
	A8	20 µg or placebo
	A9	40 µg or placebo
	A10	80 µg or placebo
	A11	160 µg or placebo
Part B	B1	TBC or placebo
	B2	TBC or placebo
	B3	TBC or placebo
	B4	TBC or placebo
	B5*	TBC or placebo
	B6*	TBC or placebo

Abbreviations: TBC = to be confirmed
* groups to be included if required.

In Parts A and B, there should not be an increase of > 3-fold between dose levels above 120 ng.

Since predictions of human exposure of OLP-1002 suggest that OLP-1002 concentrations may not be quantifiable and human data have been estimated from a single species, it is proposed that the highest dose in the multiple-ascending-dose part will be up to 50% of the highest dose in the single-ascending-dose part (ie, if the highest dose in the single-ascending-dose part is 160 µg, the highest dose in the multiple-ascending-dose part will be 80 µg). Therefore, if the predicted accumulation of 3.7-fold occurs, the highest exposure in Part B will not exceed ~2-fold the maximum exposure in the single-ascending-dose part.

Group B4 may be dosed concurrently with Group A10 (80 µg), following the dose escalation meeting for Group A9 (40 µg). The predicted C_{max} and AUC_{0-∞} for a single dose of 40 µg are 0.258 ng/mL and 1.673 ng.h/mL, respectively (Table 1). Assuming 3.7-fold accumulation, the predicted C_{max} and AUC_{0-∞} at the 20 µg dose level in Group B4 are 0.294 ng/mL and 3.15 ng.h/mL, respectively (Table 2). Exposure in Group B4, therefore, is not predicted to exceed ~2-fold the maximum exposure in Group A9.

If additional groups (B5 and B6) are required, the predicted systemic exposure will not exceed that stated in the dose escalation stopping criteria [Section 3.7]) based on available PK data.

Details of all doses administered in Parts A and B of the study will be documented in the TMF.

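### The Part B same-day dosing sentence in Section 3.4.1 uses a looser comparator than the sentinel trigger, and the two can conflict for Group B4

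*Protocol*

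**What the plan says.** The Part B sentinel trigger is stated in Section 3.1.2 and repeated in Section 3.4.1. One active and one placebo subject go first at any dose level whose steady-state exposure "is predicted to exceed exposures that have been shown to be safe and well tolerated in earlier groups in Parts A or B". When sentinels are used, Section 3.4.1 says the pair "will be dosed 4 days prior to the remaining 6 subjects".

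Later in the same paragraph of Section 3.4.1 comes the rule for groups without sentinels: "Subjects in groups where exposure is not predicted to exceed that tested in Part A will be dosed on the same day". The paragraph closes with a default for unmeasurable plasma levels: "If it is not possible to quantify exposure it will be assumed that multiple dosing results in a 4-fold accumulation".

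Section 3.5.3 adds an optional schedule. After the A9 escalation meeting, "Group B4 may be dosed concurrently with Group A10". It sets B4's predicted exposure beside A9's and concludes: "Exposure in Group B4, therefore, is not predicted to exceed ~2-fold the maximum exposure in Group A9". It does not say whether B4 will have sentinels.

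**The concern.** The two sentences in Section 3.4.1 look like the two halves of one rule, but they do not share a comparator. The trigger asks whether predicted exposure goes beyond what earlier groups, in either part, have been shown to tolerate. The same-day sentence asks only whether it goes beyond what has been tested in Part A. It does not require that the Part A group be earlier, reviewed or found safe. Both sentences are mandatory, and nothing says which prevails.

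The difference is harmless while Part A groups are completed and reviewed before the Part B group that relies on them. It matters when a Part B group runs beside a higher Part A group, which is the overlap Section 3.5.3 permits for B4 and A10. What is at stake is how many people first go beyond reviewed exposure: one active sentinel, or all six active subjects of B4 together.

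**Working it through.** **Inputs.** Section 3.5.2: in the monkey, 5.06 µg/kg gave a Cmax of 1.96 ng/mL and an AUC of 12.7 ng.h/mL; scaling is linear in dose to a 60 kg human; accumulation factors are 2.28 (Cmax) and 3.76 (AUC). Section 3.5.3: accumulation of 3.7-fold; A9 = 40 µg, A10 = 80 µg, B4 = 20 µg per dose. Section 3.4.1: 4-fold default, half-life 180 h. Section 3.1.2: doses on Days 1, 4, 7, 10 and 13.

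**1. Reproduce the protocol's predictions.**
- Cmax per µg = 1.96/5.06/60 = 0.006456; AUC per µg = 12.7/5.06/60 = 0.04183.
- A9: 0.258 ng/mL and 1.673 ng.h/mL. A10: 0.516 and 3.347.
- B4: 20 × 0.006456 × 2.28 = 0.294 ng/mL; 20 × 0.04183 × 3.76 = 3.146 ng.h/mL.

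All agree with Tables 1 and 2 and Section 3.5.3 after rounding.

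**2. Compare B4 at steady state with each Part A group.** Scaling is linear, so each ratio is 20 × factor / (40 or 80).

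| Accumulation factor | B4 / A9 (reviewed) | B4 / A10 (concurrent) |
|---|---|---|
| 2.28 (Cmax) | 1.14 | 0.57 |
| 3.76 (AUC) | 1.88 | 0.94 |
| 3.7 | 1.85 | 0.925 |
| 4 (default) | 2.00 | 1.00 |

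Every ratio to A9 exceeds 1, so the trigger requires sentinels unless an earlier reviewed Part B group covers the exposure. No ratio to A10 exceeds 1, so the same-day condition is met if A10 counts as tested.

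**3. Which factor would apply.** Section 3.4 says the assay "has delivered an LLOQ of around 1 ng/mL with the limit of detection being 0.2 ng/mL". Predicted Cmax for A9, B4 and A10 (0.258, 0.294 and 0.516 ng/mL) is below that LLOQ, so the 4-fold default would probably govern. B4 then equals A10 exactly, which still does not exceed it. This is a boundary case: a 180 h half-life with 72 h dosing gives 1/(1 − 2^(−72/180)) = 4.13-fold, and 20 × 4.13/80 = 1.03, at which the loose reading no longer applies.

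**4. Could an earlier Part B group cover B4?** Doses for B1 to B3 are still to be confirmed. If they were at most 10 µg (an assumption: half the former 20 µg Part A maximum), predicted exposure is 10 × 0.006456 × 2.28 = 0.147 ng/mL and 10 × 0.04183 × 3.76 = 1.57 ng.h/mL. Both are below A9, so they would not cover B4.

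**5. When B4 would pass A9.** Assume geometric accumulation to factor R, with r = 1 − 1/R. The ratio after n doses is (1 + r + … + r^(n−1)) × 20/40.

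| R | Dose 1 | 2 | 3 | 4 | 5 |
|---|---|---|---|---|---|
| 2.28 (Cmax) | 0.50 | 0.78 | 0.94 | 1.03 | 1.08 |
| 3.76 (AUC) | 0.50 | 0.87 | 1.14 | 1.33 | 1.48 |
| 4 (default) | 0.50 | 0.88 | 1.16 | 1.37 | 1.53 |

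B4 passes A9 at dose 3 on AUC or under the default, and at dose 4 on Cmax.

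**6. What sentinels change.** With a 4-day lead, the active sentinel has doses 3 and 4 on Days 7 and 10. The other five active subjects are dosed on Days 5, 8, 11, 14 and 17 of the sentinel calendar, so they reach dose 3 on Day 11. Without sentinels, all six active subjects reach dose 3 together.

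**The case against.** The best reply is that the conflict needs a strained reading. A group still being dosed is being tested; it has not been tested. If the word means completed and reviewed, the comparator is A9 and both sentences point to sentinels. Section 3.5.3 supports this, since it ties B4 to the A9 meeting and measures it only against A9. The trigger is also stated twice, is clear on its own and gives the safe answer. In one respect the same-day sentence is stricter, because it does not count earlier Part B groups.

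The practical controls are real too. B4's first dose is half of A9's, and on Cmax B4 passes A9 by at most 8% within the five doses. A dose-escalation meeting precedes each group (Section 3.6). Subjects dosed on one day are at least 10 minutes apart, and continuing to the rest of the group is at the Investigator's discretion (Section 3.4.1). Section 3.1.2 adds: "Prior to each dosing occasion a physician will review the available safety and tolerability data from each subject".

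All of this stands as a limit on severity, but it does not remove the inconsistency. No text says which sentence prevails or whether B4 has sentinels. Section 3.5.3 accepts B4 at up to about twice A9 without drawing the consequence for sentinel dosing. Even if tested means completed, the sentence still omits the condition that the exposure was found safe and well tolerated.

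**Conclusion.** The concern holds, as a minor point. Under the B4/A10 overlap that the protocol permits, the two sentences can give opposite instructions. B4 is predicted at 1.14 times (Cmax) and 1.88 times (AUC) the highest reviewed single-dose exposure, or 2.0 times at the 4-fold default. It is at or below A10 for every accumulation factor the protocol uses.

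This rests on three conditions: B4 starts before A10 is reviewed, no earlier reviewed Part B group covers B4's exposure, and tested is read to include a group still in progress. If any of these fails, the two sentences agree for B4. Possible harm is bounded by the controls above and by predicted NOAEL margins at 20 µg of 24.9/0.294 = 85-fold (Cmax) and 128/3.146 = 41-fold (AUC). The reason to correct it is that it sits in an operative first-in-human dosing rule.

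**What to change.** In Section 3.4.1, give the same-day sentence the trigger's comparator: a group may be dosed on one day only where its predicted steady-state exposure stays within exposures shown to be safe and well tolerated in earlier, reviewed groups of either part. The sentence then becomes the exact complement of the trigger. With B4 beside A10, every accumulation factor used above then leads to sentinels, unless an earlier reviewed group covers the exposure.

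Optionally, state in Section 3.5.3 that B4 uses sentinels if it starts before A10's Day 10 safety review, with the same exception.

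The cost is one sentence, or two with the optional one. It adds at most about a 4-day lag for the six non-sentinel B4 subjects, and none if B4 follows A10's review or is already covered. No dose level or group size changes.

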3.4.2. Pharmacodynamic Assessment

Pharmacodynamic assessments will be conducted for subjects in Groups A2, A4, A6, A9, A10, and A11.

Human experimental pain models using healthy volunteers can be used to assess the effect of a drug or treatment under controlled clinical conditions. Capsaicin is a vanilloid responsible for the pungent taste of hot peppers. In mammalian species, capsaicin-induced pain is mediated through Group C nerve fibers following activation of vanilloid 1 transient receptor potential (TRPV1) channels⁵. Nav1.7 has been implicated in controlling neuropeptide release from C-fibers, and suppression of capsaicin-induced neurogenic flair has been demonstrated by an NA_v1.7 inhibitor⁶.

Several studies have used intradermal capsaicin for human experimental pain studies^{7,8}. It has been possible to demonstrate dose-dependent responses, with intradermal injections of

100 µg generally agreed to be the ideal dosage for these studies. Intradermal injection of capsaicin causes a brief stinging/burning pain at the injection site (spontaneous pain) followed by development of secondary hyperalgesia, which can be assessed using equipment such as Von Frey hairs. A study by Gazerani et al.⁵ found that the response was site-specific and while peak pain intensity and duration were greatest in the forehead it was found that areas of visible flare and secondary hyperalgesia were significantly larger in the forearm, making the forearm the most suitable site for experimentation.

Covance CRU, Leeds, UK in 2009 performed a validation study using intradermal capsaicin (Covance CRU Study: 9999-004) with between-subject and within-subject variability demonstrating that the assessments can be reliably conducted to assess pharmacological response.

For these reasons, it has been decided to:

- Measure both capsaicin-evoked pain and secondary hyperalgesia.
- Limit the number of capsaicin tests to 3 for each subject (pre-screening, baseline, and 48 hours postdose)
- Exclude subjects who have pain <3 or >9 (using a Visual Analogic Scale [VAS]) at the pre-screening visit from PD assessment groups.

3.5. Selection of Doses in the Study

3.5.1. Starting Dose

The rat has been identified as the most sensitive species in a 13-week SC toxicity study with a 4-week recovery phase (Covance study no. 8355564). The NOAEL was the 100 nmol/kg/dose (462.29 µg/kg/dose). This dose level resulted in C_{max} of 27.6 ng/mL and 24.9 ng/mL in males and females, respectively, and AUC₀₋₂₄ of 174 ng.h/mL and 128 ng.h/mL in males and females, respectively⁴. As the exposure was lower in the female rats these data have been used to calculate the safety margins.

The dose of 462.29 µg/kg/dose corresponds to human equivalent doses (HEDs) of 74.8 µg/kg/dose, which gives a maximum recommended starting dose (MRSD) of 444 µg for a 60-kg human and thus a 15000-fold safety margin to the proposed starting dose of 30 ng and 2.8-fold margin to the proposed maximum daily dose of 160 µg. Additionally the NOAEL dose in the cynomolgus monkey was identified as 100 nmol/kg/dose (462.29 µg/kg/dose), which gives a higher HED of 150 µg/kg/dose.

In vivo, doses of 10 pmol/kg/dose (0.0462µg/kg/dose) or less were found to inhibit peripheral acute inflammatory pain. The equivalent human dose for a 60-kg human is 44 ng, thus a dose at which minimal biological effect is anticipated has been selected as the starting dose of 30 ng.

Based on further in vivo studies in the rat (see [Section 1.2.2](#)), single doses of 10,000 pmol/kg (10 nmol/kg/dose; 46.2 µg/kg/dose) or less were found to inhibit FCA-induced inflammatory pain and there were no clinically adverse findings. The equivalent dose for a 60-kg human is 44 µg, and this is therefore a dose at which biological effect is anticipated.

